9.3.2 Covariate Assessment

For each HCP type, the following sociodemographic characteristics will be collected and used to describe the sample:

- Country
- Age group (<30, 31-45, 46-65, >65)
- Gender (male/female)
- Experience: years for physicians and in-training or not for all HCPs
- Time since last contact with a patient receiving Blincyto
- Participation in a Blincyto clinical trial

9.3.3 Validity and Reliability

Qualitative techniques will be used to ensure that the HCP questionnaires are readable, understandable and easy-to-use.

The questionnaires will be developed in English and conceptually reviewed by 5 haematologists, 3 haematology nurses and 2 pharmacists in the UK. The questionnaire will be subsequently translated and linguistically validated with 3 haematologists, 2 haematology nurses and 2 pharmacists in each of the participating countries.

During the linguistic validation interviews, trained interviewers will ask participants to complete the questionnaire while ‘thinking aloud’ and to describe their thinking and thought processes as they answer each question, each section and the questionnaire as a whole. The results will be used to optimize instructions, guidance, wording, response choices, as well as language.

A master version of each questionnaire will be generated following linguistic validation in the participating countries.

9.4 Data Sources

Data for this survey will be collected by means of three questionnaires developed specifically for physicians, nurses and pharmacists. Responses will be collected through an on-line electronic data capture (eDC) system that will be used to create the study database for analytical purposes.

The on-line questionnaire will be self-administered and can be completed at the participants’ convenience. Although participants will be advised to complete the questionnaire in a timely manner, once they start the questionnaire, they will be able to stop at any point and, at a later time, pick up where they left off, if necessary.

Approved

Participants will not be able to go back and change answers to previous questions. This restriction minimizes the likelihood of the respondent using the web or other sources to influence answers to questions. Participants will also not be allowed to access the questionnaire once it has been submitted.

Additionally, a recruitment database with the feasibility to participate and the recruitment process will be compiled during the recruitment process and also used for the description of study conduct as described in [Section 9.7](#).

9.5 Study Size

Based on precision calculations provided in [Table 2](#) and [Table 3](#), sample sizes for each survey are planned as follows:

- Physician and pharmacist surveys: the study aims to include approximately [REDACTED] physicians and [REDACTED] pharmacists to allow precisions of [REDACTED] for correct responses of 60% and 90%, respectively, for the primary endpoint question of receipt. For the score of correct responses to knowledge and behavior questions ranging from 0 to 10, a sample size of [REDACTED] would produce two-sided 95% confidence intervals with a distance from the mean to the confidence limits ranging from [REDACTED] when the estimated standard deviation ranges from [REDACTED], respectively.
- Nurse survey: the study aims to include up to [REDACTED] nurses to allow precision of [REDACTED] for correct responses of 60% and 90%, respectively, for the primary endpoint question of receipt. For the score of correct responses to knowledge and behavior questions ranging from 0 to 10, a sample size of [REDACTED] would produce a two-sided 95% confidence interval with a distance from the mean to the limits ranging from [REDACTED] when the estimated standard deviation ranges from [REDACTED] respectively.

The approach to the study sample size for the HCP surveys is governed chiefly by the assumed percentage of HCPs who correctly respond to the questions, the acceptable precision around this assumed estimate and the degree of intra-class correlation. For practical reasons, we will aim to recruit more nurses than doctors and pharmacists as more nurses are expected to have contact with patients and are more likely to participate.

Approved

Table 2. Precision of Survey for [REDACTED] Nurses and [REDACTED] Physicians and Pharmacists According to a Range of Correct Response Rates to the Primary Endpoint Question of Receipt Using the Clopper-Pearson Method

Sample size	Correct Response	Lower Limit	Upper Limit
[REDACTED]	60%	[REDACTED]	[REDACTED]
[REDACTED]	70%	[REDACTED]	[REDACTED]
[REDACTED]	80%	[REDACTED]	[REDACTED]
[REDACTED]	90%	[REDACTED]	[REDACTED]
[REDACTED]	60%	[REDACTED]	[REDACTED]
[REDACTED]	70%	[REDACTED]	[REDACTED]
[REDACTED]	80%	[REDACTED]	[REDACTED]
[REDACTED]	90%	[REDACTED]	[REDACTED]
[REDACTED]	60%	[REDACTED]	[REDACTED]
[REDACTED]	70%	[REDACTED]	[REDACTED]
[REDACTED]	80%	[REDACTED]	[REDACTED]
[REDACTED]	90%	[REDACTED]	[REDACTED]
[REDACTED]	60%	[REDACTED]	[REDACTED]
[REDACTED]	70%	[REDACTED]	[REDACTED]
[REDACTED]	80%	[REDACTED]	[REDACTED]
[REDACTED]	90%	[REDACTED]	[REDACTED]
[REDACTED]	60%	[REDACTED]	[REDACTED]
[REDACTED]	70%	[REDACTED]	[REDACTED]
[REDACTED]	80%	[REDACTED]	[REDACTED]
[REDACTED]	90%	[REDACTED]	[REDACTED]
[REDACTED]	...	[REDACTED]	[REDACTED]
[REDACTED]	60%	[REDACTED]	[REDACTED]
[REDACTED]	70%	[REDACTED]	[REDACTED]
[REDACTED]	80%	[REDACTED]	[REDACTED]
[REDACTED]	90%	[REDACTED]	[REDACTED]
[REDACTED]	60%	[REDACTED]	[REDACTED]
[REDACTED]	70%	[REDACTED]	[REDACTED]
[REDACTED]	80%	[REDACTED]	[REDACTED]
[REDACTED]	90%	[REDACTED]	[REDACTED]

Approved

Table 2. Precision of Survey for [REDACTED] Nurses and [REDACTED] Physicians and Pharmacists According to a Range of Correct Response Rates to the Primary Endpoint Question of Receipt Using the Clopper-Pearson Method

Sample size	Correct Response	Lower Limit	Upper Limit
[REDACTED]	60%	[REDACTED]	[REDACTED]
[REDACTED]	70%	[REDACTED]	[REDACTED]
[REDACTED]	80%	[REDACTED]	[REDACTED]
[REDACTED]	90%	[REDACTED]	[REDACTED]
[REDACTED]	60%	[REDACTED]	[REDACTED]
[REDACTED]	70%	[REDACTED]	[REDACTED]
[REDACTED]	80%	[REDACTED]	[REDACTED]
[REDACTED]	90%	[REDACTED]	[REDACTED]
[REDACTED]	60%	[REDACTED]	[REDACTED]
[REDACTED]	70%	[REDACTED]	[REDACTED]
[REDACTED]	80%	[REDACTED]	[REDACTED]
[REDACTED]	90%	[REDACTED]	[REDACTED]

Page 2 of 2

Table 3. Precision of Survey for [REDACTED] Nurses and [REDACTED] Physicians and Pharmacists According to Assumed Standard Deviations for the Mean Score of a Range of Correct Responses to Primary Endpoint Questions of Knowledge and Behaviour Using the Clopper-Pearson

Sample size	Expected SD around the mean score of correct responses	Precision (distance from mean to limits)
[REDACTED]	0.5	0.09
[REDACTED]	1.5	0.28
[REDACTED]	2.5	0.47
[REDACTED]	3.5	0.66
[REDACTED]	0.5	0.10
[REDACTED]	1.5	0.29
[REDACTED]	2.5	0.48
[REDACTED]	3.5	0.68
[REDACTED]	0.5	0.10
[REDACTED]	1.5	0.30
[REDACTED]	2.5	0.50
[REDACTED]	3.5	0.69

Page 1 of 2

Approved

Table 3. Precision of Survey for 90 to 110 Nurses and 40 to 60 Physicians and Pharmacists According to Assumed Standard Deviations for the Mean Score of a Range of Correct Responses to Primary Endpoint Questions of Knowledge and Behaviour Using the Clopper-Pearson

Sample size	Expected SD around the mean score of correct responses	Precision (distance from mean to limits)
	0.5	
	1.5	
	2.5	
	3.5	
	0.5	
	1.5	
	2.5	
	3.5	
	...	
	0.5	
	1.5	
	2.5	
	3.5	
	0.5	
	1.5	
	2.5	
	3.5	
	0.5	
	1.5	
	2.5	
	3.5	
	0.5	
	1.5	
	2.5	
	3.5	
	0.5	
	1.5	
	2.5	
	3.5	
	0.5	
	1.5	
	2.5	
	3.5	

Approved

Approximately [REDACTED] physicians, [REDACTED] nurses and [REDACTED] pharmacists will be recruited across all participating countries from approximately [REDACTED] centres. The number of centres may be more or less depending on recruitment.

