9.2.2 Selection and Number of Sites

Site selection and sampling strategy

The sampling frame will consist of haematology centres where Blincyto is prescribed or expected to be prescribed after its launch in each participating country. Potential sites for participation will be identified by Amgen country Regional Medical Liaison (RML)

Approved

staff. All centres in the list will be approached by RMLs to identify prescribers or potential prescribers willing to participate.

HCP selection and sampling strategy

The population for the HCP surveys will consist of haemato-oncologists, nurses and pharmacists working in haematology units. After at least one haemato-oncologist has been approached for participation, other haemato-oncologists, nurses and hospital pharmacists will be identified in the centre. Approached haemato-oncologists will also be requested to provide the name and contact details (email address or telephone number, after seeking their permission) of other haemato-oncologists, nurses who administer intravenous anti-cancer drugs and pharmacists who dispense intravenous anti-cancer drugs in their centre. In turn, identified nurses and pharmacists will be requested to provide the name and contact details of other nurses and pharmacists in their centre.

HCPs identified in each centre will be approached by [REDACTED] for participation in the surveys. Haemato-oncologists, nurses and pharmacists will be invited to participate until a cap is reached in each centre of 4 haemato-oncologists, 6 nurses and 4 pharmacists.

[figure not shown]
The number of eligible haemato-oncologists, nurses and pharmacists identified and contacted but not enrolled in the study, the number of non-respondents and the number eligible and willing to participate will be recorded.

An invitation letter will be sent by post or email with a link to the web-based questionnaire. Each invitation will include information on how to access the surveys online, and a unique participant code to ensure that the invitation is used only once. If the target level of HCPs is not reached after two emails or postal mailings, non-responding HCPs will be contacted by telephone.

The overall sampling strategy is depicted in [Figure 1](#).

Approved

Figure 1. Illustration of Sampling Strategy

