9.7.2.1 General Considerations

Categorical data will be summarized by counts and percentages. Continuous data will be summarized using number, mean, standard deviation (SD), median, quartiles, minimum and maximum and in the case of non-normally distributed data, median, range and interquartile range. Corresponding 95% confidence intervals will be reported as appropriate. No adjustment will be made for multiple comparisons or for multiple analyses. All figures will be presented to three decimal places.

The statistical analysis will include a summary of the study conduct, an assessment of HCP representativeness, a descriptive analysis and the analysis of the objectives. Site characteristics (type of centre ie, academic/non-academic) will be described.

HCP representativeness: HCPs approached for enrollment, whose demographic profile information has been collected in the recruitment database (age and gender), will be divided into:

- HCPs who agree to participate in the study
- HCPs who refuse to participate in the study after being approached
- HCPs who do not respond to invitations to participate in the study

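### Section 9.5 names intra-class correlation as a driver of study size, but the visible precision figures make no allowance for clustering within centres

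*Protocol*

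**What the plan says.** Section 9.5 of the protocol justifies the size of each survey by precision alone. It lists three governing factors: the assumed percentage of correct answers, "the acceptable precision around this assumed estimate and the degree of intra-class correlation".

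Two tables carry the calculation. Table 2 covers receipt, for a range of "Correct Response Rates to the Primary Endpoint Question of Receipt Using the Clopper-Pearson Method". Table 3 covers the mean knowledge and behaviour scores and has three columns: sample size, expected SD, and distance from the mean to the limits. Its continuation heading is legible: "Precision of Survey for 90 to 110 Nurses and 40 to 60 Physicians and Pharmacists According to Assumed Standard Deviations". The confidence level is two-sided 95%.

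Section 9.2.2 describes recruitment by centre. Approached haemato-oncologists name colleagues, nurses and pharmacists in their own centre, and those nurses and pharmacists name others. Invitations continue "until a cap is reached in each centre of 4 haemato-oncologists, 6 nurses and 4 pharmacists". The planned number of centres is blacked out, and section 9.5 adds: "The number of centres may be more or less depending on recruitment".

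For the analysis, section 9.7.2.1 says only: "Corresponding 95% confidence intervals will be reported as appropriate". Section 9.7 leaves the detailed methods to the SAP.

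**The concern.** Colleagues in one centre are likely to answer more alike than colleagues from different centres, because brochure delivery and local practice are shared. A sample of such groups carries less information than the same number of independent respondents. The protocol recognises this by naming intra-class correlation as a driver of study size, yet gives no value for it, no design effect and no effective sample size.

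The study tests no hypothesis (section 7.3), so precision is its only statistical justification for size. Section 9.9 relies on it again when it calls the precision acceptable given the rarity of the disease. If the correlation never entered the calculation, section 9.5 claims a property that its tables do not have, and its readers will expect narrower intervals than a centre-clustered sample can give.

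**Working it through.** **1. Reproducing Table 3.** Three blocks of four precision values are legible, for SD 0.5, 1.5, 2.5 and 3.5. Their sample sizes are blacked out, but the heading bounds the nurse range at 90 to 110. The half-width for independent observations is t(0.975, n−1) × SD / √n.

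| n tried | t quantile | Computed half-widths | Table 3 |
|---|---|---|---|
| 110 | 1.982 | 0.0945, 0.2835, 0.4724, 0.6614 | 0.09, 0.28, 0.47, 0.66 |
| 105 | 1.983 | 0.0968, 0.2903, 0.4838, 0.6773 | 0.10, 0.29, 0.48, 0.68 |
| 100 | 1.984 | 0.0992, 0.2976, 0.4961, 0.6945 | 0.10, 0.30, 0.50, 0.69 |

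All 12 values agree to two decimals. Searching over n, the first block fits only 109 to 112, the second only 105 and the third only 100. With the normal quantile 1.96, no integer n fits the third block. (The Table 3 title names Clopper-Pearson, but the values are t intervals for a mean.)

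**2. Is a design effect hidden in these values?** The design effect is DE = 1 + (m − 1) × ICC, with m respondents per centre, and it multiplies the half-width by √DE. With n no larger than 110, the first block leaves room for a DE of at most about 1.01. At 6 nurses per centre that is an ICC of about (1.01 − 1)/5 = 0.002. Taken alone, the second and third blocks would also fit n = 110 with DE 1.05 and 1.10, but no common DE above about 1.01 fits all three. The plain reading is n = 110, 105, 100 with DE = 1.

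**3. Receipt.** The Table 2 limits cannot be checked. The Clopper-Pearson interval treats the count as binomial, that is, respondents as independent.

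**4. Size of the effect.** Neither the ICC nor the mean number per centre is stated, so both are assumed: ICC 0.05 to 0.2, and m at the section 9.2.2 caps, with 3 per centre as a smaller case for nurses. For physicians and pharmacists n = 50 is assumed, the midpoint of 40 to 60. Receipt is 60%, and Clopper-Pearson limits are computed at the effective size n/DE.

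| Group | m | ICC | DE | n/DE | 95% limits (%) | Half-width (points) |
|---|---|---|---|---|---|---|
| Nurses, n = 100 | – | 0 | 1 | 100 | 49.7–69.7 | ±10.0 |
| | 3 | 0.05 | 1.10 | 90.9 | 49.2–70.1 | ±10.5 |
| | 6 | 0.05 | 1.25 | 80.0 | 48.4–70.8 | ±11.2 |
| | 6 | 0.1 | 1.50 | 66.7 | 47.3–71.8 | ±12.3 |
| | 6 | 0.2 | 2.00 | 50.0 | 45.2–73.6 | ±14.2 |
| Physicians or pharmacists, n = 50 | – | 0 | 1 | 50 | 45.2–73.6 | ±14.2 |
| | 4 | 0.05 | 1.15 | 43.5 | 44.0–74.5 | ±15.2 |
| | 4 | 0.2 | 1.60 | 31.2 | 41.0–77.0 | ±18.0 |

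For mean scores the same √DE applies. For nurses at n = 110 and SD 3.5, the tabulated 0.66 becomes 0.6614 × √1.25 = 0.74 at ICC 0.05 with 6 per centre.

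**5. Coverage if unadjusted intervals were used.** Beta-binomial simulation of the plain Clopper-Pearson interval at 60% receipt gives about 94.8% for 100 nurses at 3 per centre and ICC 0.05. For 50 respondents at 4 per centre and ICC 0.05 it gives about 95.9%. For 100 nurses at 6 per centre it falls to about 93% at ICC 0.05, 90% at 0.1 and 85% at 0.2.

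**The case against.** Several points on the other side stand.

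- **The evidence is partial.** Only nurse-range rows of Table 3 are legible. Table 2, the Abstract figures and the physician and pharmacist rows are blacked out. For those, the lack of adjustment is inferred from the named method and the shared table layout.
- **The size is assumed.** The caps are maxima, the number of centres is hidden, and no ICC is given. With few respondents per centre the loss is small.
- **The design effect may overstate the loss.** Section 9.2.2 says every listed centre is approached. If most take part, variation between centres adds less sampling error than the formula implies. Participation will be incomplete, so this mitigates the problem without removing it.

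A reader might infer that the study's reported 95% intervals will cover too seldom. The protocol does not support that as a certainty. It fixes no interval method for the analysis, and the SAP may already treat centre as the cluster. Even unadjusted, the conservatism of Clopper-Pearson absorbs modest clustering, as step 5 shows.

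A reader might also infer that the success reading fails, because at 110 nurses and 60% receipt the lower limit moves from 50.2% to 49.0% (6 per centre, ICC 0.05). But section 8.2 speaks of a majority of participating professionals, ties it to no confidence limit, and reads it alongside other information.

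None of this answers the narrower point. Section 9.5 names a governing factor that its legible figures leave out, and a later SAP would not change those figures.

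**Conclusion.** The point holds and should be fixed, but it does not invalidate a descriptive study. The legible Table 3 values assume independent respondents, contrary to what section 9.5 says governs the sample size. The method named for Table 2 makes the same assumption. The stated precision is therefore too favourable for any material positive ICC.

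Over the assumed range, half-widths for receipt are about 5% wider (3 nurses per centre, ICC 0.05, √1.10) to 41% wider (6 nurses per centre, ICC 0.2, √2). For physicians and pharmacists at 4 per centre they are about 7% to 26% wider (√1.15 to √1.60). These are scenarios, not estimates. They rest on the assumed ICC, equal cluster sizes, n = 50 for the smaller groups, and centres behaving like a sample from a larger population. Under-coverage of the final intervals depends on the SAP using unadjusted methods as well as on the ICC and cluster size.

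**What to change.** Restate the precision in the Abstract, section 9.5 and Tables 2 and 3 using 1 + (m − 1) × ICC. Give the ICC range assumed (for example 0.05, 0.1 and 0.2), and show results at both the expected mean and the maximum number of respondents per centre. In section 9.7.2.1, state that 95% intervals treat centre as the cluster, unless the SAP already does so.

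The cost is some wording and two recalculated tables. No respondents are added, and recruitment and the questionnaires are unchanged. The stated precision will look less favourable.

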9.6 Data Management

A data management plan (DMP) will be written to guide of all aspects of data handling. It will include all data forms and annotations, testing documentation and summaries, database documentation, merging of datasets and transfer of files into SAS for statistical analysis.

Data managers and other staff at [REDACTED] will perform user acceptance testing before the eDC questionnaires and eCRF are released to study participants.

All data collected during the survey will be held confidentially. As discussed in [Section 10.3](#) the identities of HCPs taking part in the survey will be controlled by the use of unique identification codes. These source ID numbers will be held securely, and these data will be used solely for the purpose of identifying whether the HCP has completed the survey.

9.6.1 Obtaining Data Files

Survey responses will be collected in the online eDC system. The study database will be transferred to SAS for analysis.

9.6.2 Linking Data Files

In addition to the online questionnaires, the feasibility and recruitment process will be registered in a excel database and managed by the study operations staff involved in the recruitment of participants. As described in [Section 10.3](#), a unique code will be assigned to each HCP, which will be used to link the questionnaire with the recruitment database which will be kept by [REDACTED]

9.6.3 Review and Verification of Data Quality

This study is only intended to collect HCPs opinion through an on-line survey questionnaire and not clinical data, it is not planned to generate queries in the study.

9.7 Data Analysis

Statistical analyses will be mainly descriptive. A detailed statistical analysis plan (SAP) will be developed before final database lock and will include methods of analysis and presentation and table shells. All analyses will be performed using SAS 9.3 (or higher) statistical software (SAS, Cary, North Carolina, USA).

Approved

9.7.1 Planned Analyses

9.7.1.1 Primary Analysis

The primary analysis will be performed at one point in time, once the database is locked for analysis, and will address all the study objectives as described below.

9.7.2 Planned Method of Analysis

The study endpoints will be addressed using descriptive statistics.

9.7.2.1 General Considerations

Categorical data will be summarized by counts and percentages. Continuous data will be summarized using number, mean, standard deviation (SD), median, quartiles, minimum and maximum and in the case of non-normally distributed data, median, range and interquartile range. Corresponding 95% confidence intervals will be reported as appropriate. No adjustment will be made for multiple comparisons or for multiple analyses. All figures will be presented to three decimal places.

The statistical analysis will include a summary of the study conduct, an assessment of HCP representativeness, a descriptive analysis and the analysis of the objectives. Site characteristics (type of centre ie, academic/non-academic) will be described.

HCP representativeness: HCPs approached for enrollment, whose demographic profile information has been collected in the recruitment database (age and gender), will be divided into:

- HCPs who agree to participate in the study
- HCPs who refuse to participate in the study after being approached
- HCPs who do not respond to invitations to participate in the study

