9.3 Variables

The surveys will examine the effectiveness of the educational materials targeting physicians, nurses and pharmacists about the risks associated with Blincyto treatment and the best course of action to undertake in order to minimise these risks.

Three questionnaires will contain multiple-choice questions with no free text fields.

Approved

The questionnaire will be structured as follows:

- A. Acceptance to participate (date and signature)
- B. Screening: eligibility, demographics
- C. Main questionnaire domains

Section B (Screening) will collect socio-demographic characteristics (age group, gender and experience) about HCPs to explore factors associated with understanding and implementation of key messages. The questionnaire will be designed to take a maximum of 15 minutes to complete.

The questionnaire will assess the following key concepts related to each of the brochures:

- Receipt of the brochures.
- Knowledge and understanding of key messages.
- Behaviors outlined in the brochures including the distribution of educational brochures to patients/caregivers.
- Usage of the brochures ie, whether HCPs read and refer to the educational materials and reasons for not reading them.

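### The comparison of participating, refusing and non-responding HCPs uses only age and gender, and the protocol describes no way of obtaining either from those who do not take part

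*Protocol*

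**What the plan says.** Under HCP representativeness, Section 9.7.2.1 says that "HCPs approached for enrollment, whose demographic profile information has been collected in the recruitment database (age and gender), will be divided into" three groups. The third is "HCPs who do not respond to invitations to participate in the study". No other comparison variable is named. The sentence before it says that centre type (academic or not) will be described, but does not tie this to the three groups.

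On how HCPs are found, Section 9.2.2 has the sponsor's regional liaison staff list the centres and approach them for willing prescribers. Approached haemato-oncologists are asked to "provide the name and contact details (email address or telephone number, after seeking their permission) of other haemato-oncologists", and likewise of nurses and pharmacists, who are then asked to name further colleagues.

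On demographics, Section 9.3 says "Section B (Screening) will collect socio-demographic characteristics (age group, gender and experience) about HCPs". Section B follows acceptance in Section A, and Section 10.1 bars decliners from the questionnaire. Section 9.3.2 gives the bands as "Age group (<30, 31-45, 46-65, >65").

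Other information on selection is planned. Section 9.2.2 counts contacted HCPs who do not enrol and those who do not respond. Section 9.7.2.3.1 reports recruitment rates. Section 8.2 brings response rate and recruitment into the interpretation. Section 9.9 concedes that refusals may limit representativeness.

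**The concern.** One of the research questions in Section 8 is whether the brochures reached their target population. Centres come from a sponsor list and HCPs from colleagues' referrals, so those who answer may be closer than others to the sponsor's educational programme, and reported receipt may be too high. The three-group table is the one planned analysis that could show whether participants differ from the rest. If age and gender are mostly missing for refusers and non-respondents, it will compare participants with a small and unusual remainder. A table showing no difference would then be weak reassurance, yet could be read as strong.

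**Working it through.** No figure in the protocol is in dispute, so there is none to reproduce. The check sets the sections side by side and then illustrates the scale.

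**1. Where age and gender could come from**

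| Source described | What it yields | Refusers | Non-respondents |
|---|---|---|---|
| Colleague referral (9.2.2) | Name, email or telephone | No age or gender listed | No age or gender listed |
| Questionnaire Section B (9.3) | Age group, gender | Cannot open it (10.1) | Not reached |
| Recruitment database (9.4, 9.6.2) | Feasibility and recruitment process; no demographic field named | Not stated | Not stated |
| Telephone contact (9.2.2), only if the target is missed after two mailings | Content not stated | Possible, not stated | Possible, not stated |

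For participants, the unique code in Section 9.6.2 links questionnaire and recruitment database, so their age group and gender can be carried across. No equivalent is described for the other two groups.

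**2. How far non-response could move receipt**

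Let p be receipt among responders (60% and 90%, the planning values in Section 9.5) and r the response rate (assumed; the protocol gives none). Treat everyone approached as eligible. Receipt among all approached then lies between r·p, if no non-responder received the brochure, and r·p + (1 − r), if all did.

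| r (assumed) | p = 60% | p = 90% |
|---|---|---|
| 20% | 12% to 92% | 18% to 98% |
| 30% | 18% to 88% | 27% to 97% |
| 50% | 30% to 80% | 45% to 95% |
| 70% | 42% to 72% | 63% to 93% |

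The lower bound falls below one half when r < 0.5/p: 0.5/0.9 = 55.6% and 0.5/0.6 = 83.3%. For p = 90%, receipt among non-responders that would bring the overall figure down to 50% is (0.5 − 0.9r)/(1 − r): 40% at r = 20%, 33% at r = 30%, 10% at r = 50%. At r = 70% the result is negative, so it cannot happen.

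A milder case, all inputs assumed: with half responding, 80% receipt in responders and 50% in the rest, the true figure is 0.5 × 80% + 0.5 × 50% = 65%, so the survey overstates it by 15 points.

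**3. What a sparse table can show**

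Assume 50 participants (inside the 40 to 60 physicians and pharmacists in the title of Table 3), a 50% gender split, and n0 non-participants with gender recorded. The 95% half-width for the difference is 1.96 × √(0.25/50 + 0.25/n0):

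| n0 | 5 | 10 | 20 | 40 | 100 |
|---|---|---|---|---|---|
| Half-width (points) | 46 | 34 | 26 | 21 | 17 |

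The normal approximation is rough at the small values, but with ten recorded non-participants even a gap of about 30 points would not stand out.

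**The case against.** A reader might infer that recruiters hold no age or gender for non-respondents, or that the table will be almost empty. The protocol says neither. Section 9.7.2.1 presupposes that some profiles are recorded, and the referral details in 9.2.2 are what a colleague passes on, not necessarily all that is logged. Liaison staff may know more about the physicians they list, and telephone contact could supply data. Sections 9.2.2 and 9.7.2.3.1 also speak of eligible HCPs before enrolment, which suggests some capture at recruitment. What stands is that no route is described, not that none exists.

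A reader might also infer that this is the plan's only check on selection. It is not, given the counts, recruitment rates, centre description and stated limitation. But these measure the amount of non-response or describe who took part; none compares the characteristics of the three groups.

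Further variables could be added in the SAP, which Section 9.7 promises before database lock and which is not at hand. That is fair for table layout. It does not help with a field such as identification route, which may not be recoverable if it is not logged during recruitment.

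Contact round is a tempting fourth variable for the three-group table. It would be close to circular there, because the round reached largely reflects whether the HCP responded. It is useful only among respondents.

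Finally, the 80%, 50% and 50% inputs are invented and show only that non-response can bias a survey. That is accepted; they indicate the stakes, not the likely bias.

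**Conclusion.** The point holds in this form: the planned comparison is confined to age and gender and to HCPs with both recorded, and no described source provides them for refusers or non-respondents. Sparse data in those groups are likely, but how sparse cannot be derived from the protocol, which gives no response rate and no expected number with data. The ranges above rest on assumed response rates. They show that at 90% reported receipt, a response below about 56% leaves open whether a majority of those approached received the brochure, and Section 8.2 reads success from a majority among participants. The descriptive analyses remain valid for those who took part; what is weakened is the basis for extending them to the target population. The gap at age 30 is a separate small slip in the same demographic variable.

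**What to change.** In Section 9.7.2.1:

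- State how age and gender are obtained for refusers and non-respondents, and report how many in each group have them.
- Within each of the three professional surveys, compare participants, refusers and non-respondents on country and centre type (academic or not), which follow from how HCPs are identified. Add identification route (liaison list or colleague referral) if it is logged from the start of recruitment.
- Among respondents, compare receipt, knowledge and behaviour between those who answered after the mailings and those who answered only after telephone contact. This is possible only where telephone contact was used, and it treats late respondents as a rough proxy for non-respondents.
- Give the response rate as a range. Referral of nurses and pharmacists rests on handling intravenous anti-cancer drugs, while inclusion requires Blincyto experience (9.2.3.1), so the eligibility of some non-respondents may be unknown. With R respondents, E other HCPs known to be eligible and U of unknown eligibility, the range is R/(R + E + U) to R/(R + E).

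In Section 9.3.2, correct the bands so that age 30 is covered, for example ≤30, 31-45, 46-65, >65.

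The cost is a few recruitment-database fields and one or two extra tables, with no additional respondents. One limit remains: HCPs whom nobody lists or refers are in no group, so these comparisons cannot detect selection before the approach.
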